4.2 Scientific Rationale for Study Design

The randomized, controlled, examiner-blind, parallel group design selected for this DH study follows published guidance for the design and conduct of studies investigating the clinical efficacy of anti-sensitivity products ([Holland, 1997](#)). In line with these same recommendations, two independent, controllable DH stimuli (tactile and thermal) will be employed to assess the performance of the 5% CSPS toothpaste, with the least severe stimulus (tactile) applied first ([Holland, 1997](#)). To avoid inter-examiner variability, the same clinical examiner will administer a given stimulus (tactile and/or evaporative (air)) and assess its associated DH measure (tactile threshold (g) or Schiff sensitivity score) throughout the study.

DH will be clinically assessed at Screening and Baseline (pre-treatment) to determine suitability to participate and confirm subject qualification, and again after 3-, 7-, 14-, 28- and 56-days treatment to evaluate the efficacy of the Test Toothpaste with twice-daily use. At all post-Baseline time points, the anti-sensitivity efficacy of the Test Toothpaste will be compared with that of a Reference Toothpaste - a conventional, daily use fluoride toothpaste with no known anti-sensitivity efficacy (i.e., a non-desensitising toothpaste will act as negative control). Qualifying subjects will be randomized to one of the two investigational treatments using a 1:1 allocation ratio.

- Day 56 has been selected as the primary time point to confirm the anti-sensitivity efficacy of the investigational 5% CSPS toothpaste with twice daily use; 56-day (8-week) study duration is accepted as appropriate to evaluate the long-term efficacy of most anti-sensitivity products ([Holland, 1997](#)).
- Evaporative (air) is a thermal stimulus representative of the impact of chilled foods and drinks, or an intake of cold air, on sensitive teeth. ‘Cold’ is reported to be the most common stimuli for DH pain ([Fischer, 1992](#); [Flynn, 1985](#); [Gillam, 2002](#)). Thus, change from Baseline in Schiff sensitivity score at Day 56 has been selected as the primary endpoint, with study success defined as statistically significant, superior anti-hypersensitivity efficacy for the 5% CSPS toothpaste, compared to negative control, as measured by Schiff sensitivity score at Day 56 (Week 8).

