Clinical trials evaluating pain-related endpoints can be prone to ‘placebo effects’ ([Addy, 1985](#); [West, 1997](#)); such effects are frequently observed in DH studies. A study conducted to evaluate the natural history of the DH condition also highlighted the existence of a ‘no treatment’ effect, characterized by an improvement in sensitivity simply as a result of study participation ([Leight, 2008](#)). To help minimize the potential impact of such effects, an acclimatization period (14-28 days duration) will precede the Baseline visit. During this period, study subjects will brush twice daily with the regular fluoride toothpaste and toothbrush provided (in place of their own oral hygiene products) and record each brushing occasion in a diary. The acclimatization period will also serve to standardize oral hygiene practice across the study population and familiarize participants with several important study procedures (e.g., toothpaste dosage, timed brushings, diary completion) prior to treatment.

DH is an episodic condition; symptoms are known to vary spontaneously ([West, 2008](#), [West, 2013](#)). Baseline clinical values that would support enrolment may represent random highs that could be followed by regression to the mean, leaving the subject or selected test tooth without the condition under investigation (i.e., DH) during the treatment period. To help minimize the potential for this to occur in the current study, randomized subjects will be required to demonstrate consistency in response to both DH stimuli at both the Screening and Baseline visits. Qualifying subjects will have a minimum of two eligible teeth with a tactile threshold \leq 20g and a Schiff sensitivity score ≥ 2 at both Screening and Baseline. In line with published guidelines for the design and conduct of studies investigating the clinical efficacy of anti-sensitivity products, inconsistent responders will be excluded ([Holland, 1997](#)).

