5.2 Inclusion Criteria

Each individual subject must meet all the following inclusion criteria to be eligible to participate in the study.

1. Subject provision of signed and dated informed consent before any study procedures are performed.
2. Subject is male or female.
3. Subject is 18 to 65 years of age, inclusive, at the time of signing the informed consent.
4. Subject is willing and able to comply with the study visit schedule, product usage instructions, lifestyle restrictions and other study procedures.
5. Subject is in good general, oral and mental health with, in the opinion of the investigator or medically qualified designee, no clinically significant or relevant abnormalities in self-reported medical history, or upon oral examination, that would impact their safety or wellbeing, or the outcomes of the study, if they were to participate in the study, or affect their ability to understand and follow study requirements.

6. SCREENING (Visit 1)

Subject must have:

- a) History of tooth sensitivity lasting more than six months but not more than 10 years (self-reported).
- b) Good general oral health, with a minimum of 20 natural teeth.
- c) Minimum of 2 accessible, non-adjacent teeth (incisors, canines, premolars), in different quadrants, which meet all of the following criteria:
 - Exposed dentin due to facial/cervical erosion, abrasion or gingival recession (EAR).
 - MGI = 0 directly adjacent to the exposed dentin (i.e., the test area only) ([Lobene, 1986](#)).
 - Clinical mobility = 0 ([Laster, 1975](#)).
 - Clinically confirmed DH to both tactile and evaporative (air) stimuli:
 - Qualifying tactile threshold $\leq 20\text{g}$
 - Qualifying Schiff sensitivity score ≥ 2 .

7. BASELINE (Visit 2, Pre-Treatment)

Subject must have a minimum of two, non-adjacent accessible teeth (incisors, canines, premolars), in different quadrants, with clinically confirmed DH to both tactile and evaporative (air) stimuli at both Screening (Visit 1) and Baseline (Visit 2).

- Qualifying tactile threshold $\leq 20\text{g}$ at Screening & Baseline
- Qualifying Schiff sensitivity score ≥ 2 at Screening & Baseline

The clinical examiner will select two 'Test Teeth' from those which meet the tactile threshold and Schiff sensitivity score inclusion criteria at both Screening and Baseline.

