1.4 Sample Size Calculation

Sufficient subjects will be screened and entered into the acclimatization period to randomize approximately 234 subjects to study product (approximately 117 subjects per treatment group) to ensure approximately 210 complete the study (approximately 105 subjects per treatment group), allowing for approximately 10% dropouts.

The study will be sufficiently powered to demonstrate statistical superiority of the Test Toothpaste compared to the Reference Toothpaste (negative control) for the change from Baseline in the Schiff sensitivity score after 56 days, i.e., 8 weeks, (primary objective) and 3 days (key secondary objective, earliest time point) treatment. It is anticipated that the treatment effect will increase over time. A sample size of 105 evaluable subjects per treatment group will provide 90% power to detect a mean difference of 0.25 units (SD = 0.55) in change from Baseline in Schiff sensitivity score after 3 days treatment, using a 2-tailed 2-sample t-test with a 5% significance level. The sample size calculation was performed using PASS software version 23.0.1.

The dropout rate and SD estimates are based on the results of DH efficacy studies of similar design and duration (Clinical Studies CCI [REDACTED] and CCI [REDACTED] sponsor data held on file, available on request).

2 Planned Analyses

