4.4.1.2 Statistical Hypothesis, Model, and Method of Analysis

The following null and alternative hypotheses will be evaluated:

- H_0 : There is no difference in change from baseline in Schiff sensitivity score in the Test Toothpaste compared to Reference Toothpaste
- H_1 : There is a difference in change from baseline in Schiff sensitivity score in the Test Toothpaste compared to Reference Toothpaste

Change from Baseline in Schiff sensitivity score at Day 56 will be analysed using a MMRM with study product, visit and [study product x visit] interaction as fixed effects, and Baseline Schiff sensitivity score as a covariate. Note that since the Baseline Schiff sensitivity score will be included as a covariate, the Baseline Schiff stratification value will not be included in the model. Subject will be included as a repeated measure with unstructured covariance matrix. Kenward-Roger's degrees of freedom approach will be applied (Kenward, 1997). The difference between the least square mean changes from Baseline for the Test Toothpaste compared to Reference Toothpaste (negative control) at Day 56 from the MMRM will be presented, along with the two-sided p-value and 95% CIs. In the event that the model does not converge on the unstructured covariance matrix, an appropriate alternative will be considered.

Using the above model, the adjusted mean change from baseline in the Schiff sensitivity score will be reported by study product along with 95% confidence intervals (CIs) and p-values testing for a non-zero change from baseline and will be provided in Table 14.2.2.2.1. Also, mean differences between Test Toothpaste compared to the Reference Toothpaste in the change from baseline in Schiff sensitivity score at Day 56 will be presented along with 95% CIs and p-values in the same Table 14.2.2.2.1.

The assumptions of normality and homogeneity of variance in the MMRM will be investigated. In case of violation of these assumptions, a suitable non-parametric test (Van Elteren Test, adjusted for the randomization stratification, Maximum Baseline Schiff sensitivity score) will be performed to assess the change from Baseline comparison (Test Toothpaste vs. Reference Toothpaste at Day 56); the results will be provided to support the MMRM results.

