4.4.2.1.1 Statistical Hypothesis, Model and Method of Analysis

The following null and alternative hypotheses will be evaluated:

- H_0 : There is no difference in change from baseline in tactile threshold (g) in the Test Toothpaste compared to Reference Toothpaste
- H_1 : There is a difference in change from baseline in tactile threshold (g) in the Test Toothpaste compared to Reference Toothpaste

Key secondary endpoint, change from Baseline in tactile threshold (g) at Day 56, will be analysed using the same MMRM method detailed in [Section 4.4.1.2](#) but with Baseline tactile threshold (g) as a covariate (rather than Baseline Schiff sensitivity score). In addition, the maximum Baseline Schiff sensitivity score of the two ‘Test Teeth’ (2 or 3) will be fitted as a fixed effect. The results will be presented in Table 14.2.3.2.1.

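### Neither efficacy model uses the Screening reading of the two Test Teeth; adding it as a covariate is a free, probably small, gain in precision

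*SAP*

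**What the plan says.** The Schiff model in SAP 4.4.1.2 (and Protocol 12.3.1) has product, visit and their "interaction as fixed effects, and Baseline Schiff sensitivity score as a covariate". The SAP leaves the stratification value out because Baseline Schiff is already there.

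The tactile model in SAP 4.4.2.1.1 (and Protocol 12.3.2) is the same "but with Baseline tactile threshold (g) as a covariate (rather than Baseline Schiff sensitivity score", and it also carries the maximum Baseline Schiff score (2 or 3) as a fixed effect.

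SAP 3.1 defines Baseline as the Day 0 (Visit 2) value. Protocol 5.2 requires Test Teeth to be chosen from those that "meet the tactile threshold and Schiff sensitivity score inclusion criteria at both Screening and Baseline", so both visits provide readings on the same two teeth. SAP 4.4.1.1 and 4.4.2.1 list the Screening values and put them to no other use.

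**The concern.** The covariate that is meant to absorb severity is coarse, because entry cuts it to three values. The protocol also regards a single reading as noisy: Protocol 4.2 states that "DH is an episodic condition; symptoms are known to vary spontaneously" and warns of regression to the mean after a chance high. The sponsor answers this by requiring a second qualifying visit, but uses that visit only as an entry gate. A second pre-randomization reading would help to separate stable severity from day-to-day noise, and it costs nothing to collect.

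Precision matters here because testing is a chain. SAP 4.4 orders ten comparisons (Schiff then tactile, at Days 56, 28, 14, 7 and 3), and one failure ends confirmatory testing at every earlier timepoint. The sample size is set on Day 3 Schiff, which is ninth in that order. No power is stated for any tactile comparison, although four of the five tactile tests gate an earlier timepoint.

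**Working it through.** **1. Values the covariates can take.**
- Schiff: each tooth is 2 or 3 at entry (Protocol 5.2, scale in 9.1.5), so the mean of two teeth is 2, 2.5 or 3.
- Tactile: the maximum force is 20 g at Visits 1–2, steps are 10 g (Protocol 9.1.4) and calibrated settings start at 10 g. Each tooth is then 10 or 20 g and the mean is 10, 15 or 20 g. This assumes that probing uses the calibrated settings; the starting force is not stated outright.
- The Screening means are limited by the same rule to the same values.

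**2. The plan's own figure.** SAP 1.4 states: "A sample size of 105 evaluable subjects per treatment group will provide 90% power". The inputs given there are a Day 3 Schiff difference of 0.25, an SD of 0.55 and a two-sided t-test at the 5% level. Allocation is made "using a 1:1 allocation ratio" (Protocol 4.2).
- Normal approximation: n = 2 × (1.960 + 1.282)² × 0.55² / 0.25² = 101.7, so 102 per group.
- Exact noncentral t: 103 per group (power 90.1%).
- At 105 per group: SE = 0.55 × √(2/105) = 0.0759, noncentrality = 0.25 / 0.0759 = 3.29, power = 90.6%.
- Dropout: 105 / 0.90 = 116.7, so 117 per group.

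The stated sample size reproduces.

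**3. How much variance the Screening mean might remove.** The documents give no correlation between Screening, Baseline and outcome, so this part rests on assumptions. For Schiff, a latent-severity model was simulated with two teeth per subject. Stable variance was split 60:40 between subject and tooth, visit noise was independent, latent values were cut to a 0–3 score, and entry was applied at both visits. Each scenario had 600,000 candidates. The change score was regressed on Baseline, then on Baseline plus Screening.

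| Single-visit reliability (assumed) | Extra variance removed, same response in all subjects | Extra variance removed, response varying (SD 0.7 latent units) |
|---|---|---|
| 0.30 | 2.5–2.7% | 1.3–1.5% |
| 0.50 | 5.9–6.3% | 2.8–2.9% |
| 0.70 | 10.4–11.0% | 4.0–4.5% |
| 0.85 | 14.9–15.1% | 4.3–4.6% |

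A second set of runs used reliability 0.5–0.9. With response SD 0.4–0.6 it gave 3–7%. With Screening also made 30% less reliable than Baseline, it gave 2–4%.

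Neither end of the range is established. The simulated SD of change was 0.45–0.70 with uniform response and 0.73–0.87 with response SD 0.7, against the plan's 0.55.

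For tactile threshold, similar runs gave about 3–15%. They compared Baseline alone with Baseline plus Screening and omitted the maximum Baseline Schiff term, so they do not measure the gain over the planned model.

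**4. What that means for power.** Take 0.55 as the residual SD before Screening is added. With variance reduction v, SD = 0.55 × √(1 − v), the SE falls by 1 − √(1 − v), and the gain is equivalent to 210 × (1/(1 − v) − 1) subjects.

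| v | SD | SE reduction | Power at 105 per group | n per group for 90% | Equivalent extra subjects on 210 |
|---|---|---|---|---|---|
| 0 | 0.550 | 0 | 90.6% | 103 | 0 |
| 1% | 0.547 | 0.5% | 90.9% | 102 | 2 |
| 4% | 0.539 | 2.0% | 91.7% | 99 | 9 |
| 7% | 0.530 | 3.6% | 92.5% | 96 | 16 |
| 15% | 0.507 | 7.8% | 94.5% | 88 | 37 |

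**5. Where the gain falls.** The plan expects the effect to grow after Day 3. If the Day 56 difference were 0.35 (assumed, same SD), power at 105 per group is already 99.6%. Any benefit therefore falls mainly on the early gated comparisons.

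**The case against.** The strongest reply is that Screening is not an equivalent replicate of Baseline. It precedes the acclimatization period, which exists to standardize oral hygiene and damp placebo and no-treatment effects (Protocol 4.1, 4.2). The pre-visit rules on hygiene, eating and drinking, and alcohol start only at Baseline (Protocol 5.5.1, 5.5.2). The reading is also truncated by the same entry rule. All of this stands. It gives a sound reason to keep Baseline as the anchor and to expect a smaller gain, but no reason to leave the reading out as an additional covariate.

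The second reply is that the choice of further covariates is a design preference and nothing in the plan is wrong. That also stands, and it sets the priority.

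A reader might go further and infer that precision is being thrown away for no reason, that both models rest on a single Baseline reading, or that the trial is biased or underpowered. The documents do not support these readings. The difference in conditions favours Baseline, the tactile model also fits maximum Baseline Schiff, randomization protects the comparison, and the sample size meets its 90% target without any covariate. Nor do they support a firm saving of 30 or more subjects, which appears only under the most favourable assumptions.

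**Conclusion.** The point holds as a missed efficiency. The planned models are valid, but a relevant pre-randomization measurement on the same teeth, scored by the same examiner for a given stimulus (Protocol 4.2), goes unused and no reason is given. The size cannot be found from the documents. Under the assumed models the Schiff residual variance falls by about 1–15%, and more likely by 1–7% if response varies between subjects. On the plan's Day 3 figures, 1–7% takes power from 90.6% to about 91–92.5%. The tactile gain over the planned model is not quantified. Priority is low.

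**What to change.** Before unblinding:
- In SAP 4.4.1.2 and Protocol 12.3.1, add the mean Screening Schiff score of the two Test Teeth as a further covariate.
- In SAP 4.4.2.1.1 and Protocol 12.3.2, add the mean Screening tactile threshold of the two Test Teeth, keeping Baseline tactile threshold and the maximum Baseline Schiff term.
- Preferably add covariate-by-visit terms, since the value of a pre-treatment reading may change between Day 3 and Day 56.
- Leave the change score anchored on Visit 2.
- Record the change in SAP section 5, which now reports none, and state how a subject randomized in error without a Screening value will be handled.

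The sponsor could first check the correlation in the earlier studies cited for the SD, if they took a comparable Screening reading. If it prefers not to alter the primary model, a pre-specified sensitivity analysis is a weaker alternative.

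The cost is a few lines of wording and one degree of freedom per model. With five post-Baseline visits, by-visit slopes add four more for each covariate given them. No new data are needed, and by design no randomized subject lacks the value.

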4.4.1.3 Supportive Analyses

If there is at least 10% difference in the overall number of subjects between PP and mITT Populations, a summary and statistical analysis of the Schiff sensitivity score will be presented

for the PP Population in Table 14.2.2.1.2 and Table 14.2.2.2.2, respectively. In addition, Schiff sensitivity score (Figure 14.2.2.1.2) at each time point will be plotted by study product in for all subjects in PP Population.

A decision on whether a PP analysis will be performed will be made prior to study unblinding (release of the randomization codes).

4.4.2 Secondary Efficacy Endpoints

4.4.2.1 Change from Baseline in Tactile Threshold (g) at Day 56

The key secondary variable is the change from Baseline in tactile threshold (g) at Day 56.

Tactile threshold (g) will be derived as the mean value for the two ‘Test Teeth’ (selected at Baseline). Change from Baseline will be derived for each individual tooth first before calculating mean change for the two ‘Test Teeth’ where change from Baseline in tactile threshold (g) at Day x is defined as [(tactile threshold at Day x) minus (Baseline tactile threshold)].

Descriptive statistics (n, mean, SD, standard error [SE], median, minimum, and maximum) will be presented for tactile threshold (g) calculated as the average score of the two test teeth at each assessment time point in Table 14.2.3.1.1 for all subjects in mITT population by study product. Raw means (\pm SE) of the tactile threshold (g) at each time point will be plotted by study product in Figure 14.2.2.2.1 for all subjects in mITT population.

Individual tactile threshold (g) data will be listed for each subject by visit and study product group in Listing 16.2.6.3 and Listing 16.2.6.4, for Screening and Baseline, and separately for two test teeth respectively, for all randomized subjects.

4.4.2.1.1 Statistical Hypothesis, Model and Method of Analysis

The following null and alternative hypotheses will be evaluated:

- H_0 : There is no difference in change from baseline in tactile threshold (g) in the Test Toothpaste compared to Reference Toothpaste
- H_1 : There is a difference in change from baseline in tactile threshold (g) in the Test Toothpaste compared to Reference Toothpaste

Key secondary endpoint, change from Baseline in tactile threshold (g) at Day 56, will be analysed using the same MMRM method detailed in [Section 4.4.1.2](#) but with Baseline tactile threshold (g) as a covariate (rather than Baseline Schiff sensitivity score). In addition, the maximum Baseline Schiff sensitivity score of the two ‘Test Teeth’ (2 or 3) will be fitted as a fixed effect. The results will be presented in Table 14.2.3.2.1.

4.4.2.1.2 Supportive Analyses

A PP analysis will be performed on the change from baseline in tactile threshold (g) as detailed in [Section 4.4.1.3](#) and the same MMRM model will be used as detailed in [Section 4.4.2.1.1](#). The results will be presented in Table 14.2.3.1.2 and Table 14.2.3.2.2 respectively for summary table and analysis table. Also, Figure 14.2.2.2.2 will be generated for all subjects in PP population.

4.4.2.2 Change from Baseline in Schiff Sensitivity Score at Day 28, Day 14, Day 7, and Day 3

The other secondary efficacy endpoint will be the change from Baseline in Schiff sensitivity score at Day 28, Day 14, Day 7, and Day 3.

The summary results for this endpoint will be obtained as detailed in [Section 4.4.1.1](#). The results will be presented in Table 14.2.2.1.1.

4.4.2.2.1 Statistical Hypothesis, Model and Method of Analysis

The analysis is same as primary endpoint and the details will be obtained from [Section 4.4.1.2](#). Also, the results will be presented in Table 14.2.2.2.1.

4.4.2.2.2 Supportive Analyses

A PP analysis will be performed on the change from baseline in Schiff sensitivity score as detailed in [Section 4.4.1.3](#) and the same MMRM model will be used as detailed in [Section 4.4.1.2](#). The results will be presented in Table 14.2.2.1.2 and Table 14.2.2.2.2 respectively for summary table and analysis table. Also, Figure 14.2.2.1.2 will be generated for all subjects in PP population.

4.4.2.3 Change from Baseline in Tactile Threshold (g) at Day 28, Day 14, Day 7, and Day 3

The other secondary efficacy endpoint will be the change from Baseline in tactile threshold (g) at Day 28, Day 14, Day 7, and Day 3.

The summary results for this endpoint will be obtained as detailed in [Section 4.4.2.1](#). The results will be presented in Table 14.2.3.1.1.

